4.2.2. Per-protocol Analysis Set (PP)

The Per-protocol analysis set (PP) will consist of all subjects in the Intent-to-treat analysis set (ITT) without any major deviation of the protocol and its procedures until the week 116/164/220 visit. Subjects with major protocol deviations (except those not effecting the secondary endpoints) will be excluded from the per-protocol analysis.

4.2.3. Nail Psoriasis Analysis Set

The change from baseline (week 0) in the Nail Assessment in Psoriasis and Psoriatic Arthritis (NAPPA) score at the respective scheduled week will be evaluated among subjects with nail psoriasis at baseline (week 0). Nail psoriasis at baseline (week 0) will be defined as follows:

- eCRF question 'Was Nail Assessment in Psoriasis and Psoriatic Arthritis (NAPPA) performed?' is answered with 'Yes'
 - if 'Yes', patient has nail psoriasis if NAPPA-CLIN ≥ 1 at baseline (week 0).

These analyses will be performed for the ITT set and, if requested, the PP set.

Update before the final analysis:

For the analysis of NAPPA-CLIN (hands), only those subjects who have a NAPPA-CLIN (hands) score ≥ 1 at Baseline (Week 0) will be included.

For the analysis of NAPPA- CLIN (feet), only those subjects who have a NAPPA-CLIN (feet) score ≥ 1 at Baseline (Week 0) will be included.

4.2.4. Safety Analysis Set

For all safety analyses, all subjects who entered groups **3a** or **3b** of Study Part 3 will be included in the Safety analysis set; hence the Safety analysis set is identical to the ITT analysis set.

Note: For study groups 3a and 3b there is no administration of study agent in Study Part 3; if treatment was started in Study Part 3 the subject is evaluated in study group **3c** for the analysis of re-treatment phase which is not covered by this SAP.

4.2.5. Pharmacokinetics Analysis Set

The PK analysis and the definition of the PK analysis set is out of scope for this SAP.

5. STATISTICAL ANALYSES FOR STUDY PART 3

Description of planned statistical analyses in Study Part 3 will focus on the comparison of the two study groups 3a and 3b which are without administration of study agent in Study Part 3 (ie, group **3a**: randomized to guselkumab 100 mg q8w in Study Part 2 vs. group **3b**: randomized to guselkumab 100 mg q16w in Study Part 2). Inferential statistics (ie, exploratory p-values, confidence intervals, etc.) will be provided only for the week 116/164/220 data of endpoints in Study Part 3.

Note 1: Statistical analysis of Study Part 3 will also include analyses of study data recorded before week 68. Data of Study Parts 1 and 2 will be summarized by descriptive statistics only. No exploratory inferential statistics (ie, p-values, confidence intervals, etc.) will be provided for the data of Study Parts 1 and 2.

Note 2: Subjects of group 3a and 3b who start re-treatment with guselkumab within Study Part 3 (up to week 116) will be evaluated only up to the study visit R0 at which PASI >5 is shown. If PASI was ≥ 3 already at week 68 the subject will not be evaluated for Study Part 3 in the scope of this SAP; a separate SAP will describe the analysis of the re-treatment phase.

5.1. General Considerations

The following general analysis definitions refer only to Study Part 3.

The statistical analysis of Study Part 3 will be exploratory. All inferential statistical testing (including calculation of confidence intervals) is to be interpreted in the exploratory sense only. There are no multiplicity adjustments, all p-values are nominal.

Descriptive statistics will include counts and proportions for categorical data, and mean, SD, median, interquartile range, and range, for continuous data. Graphical data displays will also be used to summarize the data.

The two-group large-sample normal approximation Wald Z-test with Mantel-Haenszel stratum weights for 'disease duration' will be used to compare the proportion of subjects still maintain control of disease. Continuous response parameters will be compared using a univariate analysis of covariance model with fixed effects for study group, and disease duration and baseline value as covariates. Time-to-event endpoints will be analyzed using Kaplan-Meier product limit methods to estimate the survival distributions and the median time-to-event.

In general, summary tables will be displayed by study group as the main classification variable and for the total of the sample (not for efficacy analyses) in the respective analysis set; ie, results will be provided for group **3a**, group **3b**, and total of group **3a** and group **3b** (not for efficacy

analyses). Additional classification variables are explicitly mentioned in the following text. Individual subject data listings will be presented parameter-wise and will be sorted by study group, study site, subject's identification number and study visit, if applicable. A more detailed description of the planned statistical analyses is provided in the sections below.

5.1.1. Visit Windows

As subjects do not always adhere to the protocol visit schedule, the following rules are applied to assign actual visits to analysis visits. Listed below are the visit windows and the target days for each visit. The reference day is Study Day 1 (for definition see section 5.1.3). If a subject has two or more actual visits in one visit window, the visit closest to the target day will be used as the protocol visit for that visit window. The other additional visit(s) will not be used in the summaries or analyses, but they can be used for determination of clinically important endpoints. If two actual visits are equidistant from the target day within a visit window, the later visit will be used.

All assignments will be made in chronological order. Once a visit date is assigned to a visit window, it will no longer be used for a later time point except for the endpoint. Listed below (Table 2) are the visit windows and the target days for each visit defined in the protocol.

Table 2 – Visit Windows

Parameter	Analysis Period	Scheduled Visit	Time Interval (label on output)	Time Interval (Day)*	Target Time Point (Day)
All	1	Scr	Screening	-35 to -1	
	1	W0	Baseline	-14 to 6	1
	1	W4	Week 4	15 to 43	29
	1	W12	Week 12	71 to 99	85
	1	W16	Week 16	100 to 126	113
	1	W20 %	Week 20	127 to 182	141
	1	W28 §	Week 28	183 to 238	197
	2	W36	Week 36	239 to 267	253
	2	W44	Week 44	295 to 323	309
	2	W52	Week 52	351 to 379	365
	2	W60	Week 60	407 to 435	421
	2	W68 §	Week 68	463 to 532	477
	3	W80	Week 80	533 to 589	561
	3	W92	Week 92	617 to 673	645
	3	W104	Week 104	701 to 757	729
	3	W116 # §	Week 116	758 to 868	813
	3	W128	Week 128	869 to 925	897
	3	W140	Week 140	953 to 1009	981
	3	W152	Week 152	1037 to 1093	1065
	3	W164 # §	Week 164	1094 to 1204	1149
	3	W176	Week 176	1205 to 1261	1233
	3	W188	Week 188	1289 to 1345	1317
	3	W200	Week 200	1373 to 1429	1401
	3	W212	Week 212	1457 to 1513	1485
	3	W220 #	Week 220	1513 to 1569	1541

* Relative to Study Day 1

W116, W164 and W220 are the final visits for the interim or final analyses of Study Part 3 – for these no upper border of the visit window will be applied (ie, all W116/W164/W220 visits later than the upper border will be used for analysis of the respective evaluation).

% Visit window for week 20 has been expanded after completion of the Week 116 analysis.

§ Visit windows for flagged scheduled weeks have been expanded after the Dry Run Meeting for the Week 116 analysis.

Telephone visits scheduled at weeks 74, 86, 98, 110, 122, 134, 146, 158, 170, 182, 194, and 206, will not be re-assigned, as no endpoint data are assessed at these visits.

If there are site visits outside of the defined windows above, final decisions on the allocation of the actual visit to an earlier or later planned visit or whether the data will not be included in the analysis will be made during the Data Review or Dry Run Meeting.

5.1.2. Pooling Algorithm for Analysis Centers

No pooling of centers will be performed.

5.1.3. Study Day and Relative Day

Study Day 1 or Day 1 refers to the start of the first study agent administration within Study Part 1. All efficacy and safety assessments at all visits will be assigned a day relative to this date.

Study day or relative day for a visit is defined as:

- Visit date – (date of Study Day 1) +1, if visit date is \geq date of Day 1
- Visit date – Date of Day 1, if visit date $<$ date of Day 1.

There is no 'Day 0'.

5.1.4. Baseline and Endpoint

Baseline for Study Part 3 is defined as the last observation (ie, value, measurement) prior to the start of the first study agent administration at baseline (week 0) in Study Part 1.

Endpoint for Study Part 3 is defined as the last available post-baseline result within the analysis period from week 68 until week 116/164/220. Results obtained at unscheduled visits are included in this definition and will be considered as the endpoint value if the unscheduled visit result is the last post-baseline result available within the analysis period from week 68 until week 116/164/220.

5.1.5. Imputation Rules for Missing AE Date/Time of Onset/Resolution

Partial onset dates of adverse events (AEs) will be imputed as follows:

- If the onset date of an AE is missing day only, it will be set to:
 - First day of the month that the AE occurred, if month/year of the onset of AE is different than the month/year of the study agent start
 - Day of study agent start, if the month/year of the onset of AE is the same as month/year of the study agent start date and month/year of the AE resolution date is different
 - Day of study agent start or day of AE resolution date, whichever is earliest, if month/year of the onset of AE and month/year of the study agent start date and month/year of the AE resolution date are same.

- If the onset date of an AE is missing both day and month, it will be set to the earliest of:
 - January 1 of the year of onset, as long as this date is on or after the study agent start date
 - Month and day of the [study agent start date], if this date is the same year that the AE occurred
 - Last day of the year if the year of the AE onset is prior to the year of the [study agent start date],
 - The AE resolution date.
- Completely missing onset dates will not be imputed.

Partial AE resolution dates not marked as ongoing will be imputed as follows:

- If the resolution date of an adverse event is missing day only, it will be set to the earliest of the last day of the month of occurrence of resolution or the day of the date of death, if the death occurred in that month.
- If the resolution date of an adverse event is missing both day and month, it will be set to the earliest of December 31 of the year or the day and month of the date of death, if the death occurred in that year.
- Completely missing resolution dates will not be imputed.

5.1.6. Treatment Failure Criteria

No treatment failure criteria are defined for Study Part 3 analysis.

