In Study Part 2 the two-group large-sample normal approximation Wald Z-test with Mantel-Haenszel stratum weights for 'disease duration' will be used to compare the proportion of subjects responding to treatment. The Mantel-Haenszel estimate, the two-sided 90% Wald-type confidence limits, and the test for the difference of proportions in Study Part 2 will be computed by using Mantel-Haenszel stratum weights ([Mantel und Haenszel 1959](#)) and the Sato variance estimator ([Sato 1989](#)). Continuous response parameters in Study Part 2 will be compared using an analysis of variance model with fixed effects for treatment group and disease duration and baseline value as covariate. Time-to-event endpoints will be analyzed using Kaplan-Meier product limit methods to estimate the survival distributions and the median time-to-event. Exploratory statistical analyses of response parameters in Study Part 1 and Study Part 3 will be performed analogously, as appropriate. Details will be provided in the SAP.

Non-responder imputation (for binary endpoints) or Last Observation Carried Forward (LOCF) imputation (for continuous endpoints) will be applied for subjects with missing data for the other secondary endpoints as described in Section [11.11](#).

Criteria for Endpoints

Treatment failure: Subjects who discontinue study agent due to lack of efficacy, an AE, worsening of psoriasis, or who started a protocol-prohibited medication/therapy during the study period that could improve psoriasis are considered treatment failures. Treatment failure rules (TFR) will be applied after week 68 for a separate analysis. The treatment failure rules will be documented in detail in the SAP.

PASI 75 Responders:	Subjects with $\geq 75\%$ improvement in PASI from baseline at week 28
PASI 90 Responders:	Subjects with $\geq 90\%$ improvement in PASI from baseline at week 28
PASI 100 Responders	Subjects with 100% improvement in PASI from baseline at week 28
Maintenance of control of disease	Subjects with a PASI score < 3
Fluctuating disease:	absolute PASI score 3 to 5
Loss of disease control	absolute PASI score > 5

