11.11. Handling of Missing Data

All available data will be included in the analyses and will be summarized as far as possible. If not otherwise specified, there will be no substitution of missing data, ie, missing data will not be replaced, missing data will be handled as 'missing' in the statistical evaluation ('observed cases analysis').

Non-responder imputation will be applied for subjects with missing data for the primary endpoint at week 68 as described below:

Subjects who do not maintain control of disease (absolute PASI score ≥ 3) or subjects who discontinue study treatment during the study before week 68 will be considered non-responders for the primary endpoint at week 68. In addition, subjects who do not return for evaluation at week 68 will be considered non-responders at week 68.

Non-responder imputation for the other binary endpoints will be performed analogously.

For continuous response parameters, the last available observation after baseline will be calculated and used for analysis in case of premature termination (Last Observation Carried Forward approach; LOCF).

LOCF may also be used as sensitivity analysis for binary response parameters. Treatment failure rules (TFR) will be applied after week 68 for a separate analysis. Additional sensitivity analyses may be done by applying different imputation rules for missing data (eg, 'multiple imputation'). An 'observed cases analysis' for all binary and continuous endpoints without substitution of missing data may also be used. A more detailed description of the handling of missing data will be provided in the SAP.

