5.1.8. Missing Data Imputation

Data of study endpoints from subjects who started a protocol-prohibited medication/therapy during the study period that could improve psoriasis will be set to 'missing' from that point onward. The protocol-prohibited medications/therapies are listed in section 8.1 of the CSP. For the statistical analysis of Study Part 3, protocol prohibited medication/therapy will be identified in the SDTM DV domain as DVDECOD='RECEIVED DISALLOWED CONCOMITANT TREATMENT'.

After the rule for handling of protocol-prohibited medication/therapy is applied, missing data will be handled as follows:

- Non-responder imputation for binary efficacy endpoints will be applied for subjects with missing data at any study visit.
- Last Observation Carried Forward (LOCF) imputation for continuous efficacy endpoints will be applied for subjects with missing data in Study Part 3.
 - This approach implies that a separate "endpoint" visit will be calculated that gets the imputed value, thus leaving the observed value as it is, if data are summarized descriptively only.
 - The earliest visit used for LOCF approach is the week 68 visit; no data from Parts 1 and 2 will be used as LOCF value for the week 116/164/220 visit.

- Time-to-event analyses of binary endpoints will be performed after the rule for handling of protocol-prohibited medication/therapy is applied (missing data will not be replaced for time-to-event analyses).

An 'observed cases analysis' for all binary and continuous endpoints in Study Part 3 without any imputation of missing data (ie, also not set to missing once protocol-prohibited medication/therapy is started) will also be done. These analyses will provide only descriptive statistical results and will also include by-visit data of Study Parts 1 and 2 (see section 5.6).

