5.5.3. Analysis Methods

5.5.3.1. Psoriasis Area and Severity Index (PASI)

- Proportion of subjects who achieve a PASI 75/90/100 response at weeks 116, 164, and 220

The proportion of subjects still meeting the response criteria will be displayed in frequency tables providing the number and percentage of subjects per study group (NRI and OC analysis) along with odds ratio (OR), relative risk (RR) and risk difference (RD), and two-sided Wald-type 95% confidence intervals (95% CIs) stratified by 'disease duration'. For single proportions within each study group, unstratified two-sided 95% CIs according to Clopper-Pearson will be calculated. Graphical presentation will be presented by means of bar charts.

The two-group large-sample normal approximation Wald Z-test with Mantel-Haenszel stratum weights for 'disease duration' will be used to compare the proportion of responding subjects among the study groups. The Mantel-Haenszel estimate, the two-sided Wald-type 95% confidence limits, and the test for the difference of proportions will be computed by using Mantel-Haenszel stratum weights (Mantel & Haenszel, 1959) and the Sato variance estimator (Sato 1989).

Results will also be given for the entire population. In addition, in a modified OC analysis all subjects fulfilling the criteria for re-treatment within the week 116 visit window (ie, PASI>5) will be disregarded.

- Time to loss of disease control after treatment withdrawal beyond week 68

Time-to-event endpoints will be analyzed using the Kaplan-Meier product limit method and Cox proportional hazards model. Summary tables will provide counts and percentages by study group, the median time-to-event with 95% confidence intervals (CI), and the hazard ratio (including 95% CI and the p-value calculated from Cox-regression with the factors 'study group' and 'disease duration'). The survival curves will also be displayed graphically. Time-to-event analyses of binary endpoints will be performed on the observed cases only after the rule for handling of protocol-prohibited medication/therapy is applied. (ie, missing data will not be replaced for time-to-event analyses).

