6.2. Appendix 2 Changes to Protocol-Planned Analyses

No important changes from the planned analyses specified in the protocol and its amendments were applied.

However, the time point of analyses is changed slightly. While the CSP states that “interim analyses are planned after all subjects have completed their visit at week 116 (or at week 144 in case of subjects entering the re-treatment arm in week 116) and at week 164 (or at week 192 in case of subjects entering re-treatment arm in week 164). The final analysis will be performed after all subjects have completed their visit at week 220 (or at week 248 in case of subjects entering the re-treatment arm in week 220)”, it was decided to split the analyses of group 3a/3b subjects and the analyses of group 3c subjects (re-treatment phase). By this, the results for the week 116/164/220 analyses of study groups 3a and 3b will be available as soon as possible. A separate SAP will be written for the analysis of the re-treatment phase that will include – beneath the group 3c – also the analysis of study group 2d (subjects who entered the re-treatment phase already in study part 2).

In addition, some new analyses have been added to the evaluation; see section 5.6 for details.

The initial SAP, prepared before the Dry-run meeting for the first interim analysis (week 116), was updated several times during the course of the study:

- Changes introduced before the Week 116 analysis:
 - The windows for the week 28, 68, 116, 164 and week 220 visits are expanded.
 - For LOCF, the earliest visit used for carrying forward is the week 68 visit.
 - Statistical testing for binary endpoints is also performed for the OC analysis.
 - For binary endpoints, a modified OC analysis is done to exclude visits with PASI>5.
 - Subgroups are compared by statistical testing.
 - The analysis of adverse events excluded AEs starting on the day of the R0 visit.
- Change introduced before the Week 164 analysis:
 - Demographic data are displayed separately for each subgroup.
- Changes introduced before the Week 220 analysis:
 - The subgroups C to H are not evaluated for the analysis of PASI and DLQI response.
 - For the time-to-event endpoints, subgroups I to H are added.
 - All efficacy endpoints (PASI, DLQI, PSSD, BSA, and NAPPA scores and changes from baseline) by visit are presented only for visits with PASI < 5 (OC modified), with subgroups A and B.
 - PASI and DLQI response by visit are evaluated for NRI and OC modified.

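### The treatment-failure analysis that the protocol promises after week 68 is missing from the Part 3 SAP and not listed as a departure, which leaves starters of prohibited therapy weakly handled outside the binary endpoints

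*SAP*

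**What the plan says.** **Protocol.** Section 11.3 (Criteria for Endpoints) says that subjects "who started a protocol-prohibited medication/therapy during the study period that could improve psoriasis are considered treatment failures", and that "The treatment failure rules will be documented in detail in the SAP". Section 11.11 repeats the commitment: "Treatment failure rules (TFR) will be applied after week 68 for a separate analysis". Neither section makes it optional. Neither names the endpoints that the separate analysis covers.

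**Part 3 SAP.** Section 5.1.6 reads "No treatment failure criteria are defined for Study Part 3 analysis", and 5.1.7 (Treatment Failure Rules) is marked not applicable. The Re-treatment SAP and the Overall safety SAP define no criteria either. Appendix 2 of the Part 3 SAP states "No important changes from the planned analyses specified in the protocol and its amendments were applied". It then itemises several smaller changes, such as wider visit windows and dropped PASI tables, but not this one.

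**What the Part 3 SAP does with starters of a prohibited therapy.** Under 5.1.8 their endpoint data "that could improve psoriasis will be set to 'missing' from that point onward". After that step, "Non-responder imputation for binary efficacy endpoints will be applied for subjects with missing data at any study visit". Continuous endpoints get last observation carried forward, starting no earlier than week 68. For time to loss of disease control, 5.5.3.1 says "Time-to-event analyses of binary endpoints will be performed on the observed cases only after the rule for handling of protocol-prohibited medication/therapy is applied", and 5.5.1.1 censors at the last PASI assessment. Section 5.6 adds time to end of the treatment-free period. It censors subjects without re-treatment at the analysis visit or study termination, and then applies the prohibited-therapy rule without giving a date.

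**Follow-up.** Protocol section 8 asks a subject who starts a prohibited therapy between weeks 68 and 220 to complete the week-220 visit all the same.

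**The concern.** An analysis that the protocol specifies has been left out, and the appendix meant to show such departures reports nothing important. A reader who relies on Appendix 2 would not know.

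The omission matters where no other rule makes starters failures. Protocol 10.2 gives worsening psoriasis as its example of why a subject might start a prohibited medication. If that is the reason, censoring at the start removes a subject who is close to losing control, and the Kaplan-Meier curve for a protocol endpoint is too favourable. Some starts may have other reasons, so the censoring may be informative but need not be. Carrying forward the last value before the therapy freezes a continuous score before the deterioration. For the treatment-free period, a subject on another antipsoriatic drug could be reported as treatment-free.

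**Working it through.** **1. Was the commitment in force?** The Part 3 SAP cites Amendment 5, which is not among the documents. The supplied protocol is Amendment 6. Its table of key changes lists the title page, synopsis and dosage section, and no statistical section. That Amendment 5 carried the same commitment is therefore an inference.

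**2. What happens to a starter, by type of analysis**

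| Analysis | Rule in the Part 3 SAP | Result for a starter |
|---|---|---|
| Binary endpoints, including retained control and PASI ≤5 | set to missing, then non-responder imputation (5.1.8) | failure, as a treatment-failure rule would give |
| Continuous endpoints | set to missing, then last value carried forward (5.1.8) | value from before the therapy stands |
| Time to loss of disease control | set to missing, not replaced, censored at last PASI (5.1.8, 5.5.1.1, 5.5.3.1) | censored before the start; any later PASI >5 discarded |
| Time to end of treatment-free period | dates of R0, analysis visit or termination only (5.6) | three readings fit: ignored, censored at start, or counted as the end |

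In the last row, setting endpoint data to missing has no defined effect, because the formula uses visit dates and disregards PASI.

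**3. After the therapy has stopped.** The Part 3 rule has no end point. The Re-treatment SAP, 5.1.8, uses data from R0 onward if the therapy stopped before R0. Read literally, the same R0 PASI >5 is discarded in Part 3 and serves as baseline in the re-treatment analysis.

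**4. Exact size for the treatment-free proportion.** Inputs, from the Overall safety SAP 4.5: 273 subjects entered withdrawal and 227 of them were re-treated.
- Not re-treated: 273 − 227 = 46; 46/273 = 16.8%.
- Per starter counted as a failure: 1/273 = 0.37 points.
- 5 starters: 41/273 = 15.0%. 10 starters: 36/273 = 13.2%.

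This is a crude proportion, not the planned Kaplan-Meier estimate.

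**5. Illustration for Kaplan-Meier at week 220.** The number of starters, k, is assumed. Event times follow a truncated exponential with rate −ln(46/273)/152 = 0.0117 per week. The table gives the estimate with starters censored minus the estimate with starters counted as events, in points.

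| Scenario | k = 5 | k = 10 | k = 20 |
|---|---|---|---|
| Starters among the 46, starts spread evenly over 152 weeks | 0.8 | 1.6 | 2.8 |
| Starters among the 46, start times distributed like events; all others reach week 220 | 0.6 | 1.1 | 1.8 |
| Same, 10 of the 46 ended at week 116 | 0.5 | 1.0 | 1.4 |
| Same, 20 of the 46 ended at week 116 | 0.4 | 0.7 | 0.8 |
| Starters among the 227 re-treated, later PASI >5 discarded (0 to 20 of the 46 ended at week 116) | 0.3–0.5 | 0.7–0.9 | 1.4–1.9 |

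For the treatment-free endpoint in the first scenario, the three readings (ignored / censored / counted as the end) give 16.8/15.8/15.0% with k = 5 and 16.8/12.3/9.5% with k = 20.

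**The case against.** The case on the other side is substantial, and several parts of it stand.

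- A reader might infer that the SAP hides the omission. It does not: 5.1.6 and 5.1.7 state openly that nothing is defined. What is missing is its listing as a departure.
- A reader might infer that starters pass as responders throughout Part 3. They do not. Non-responder imputation fails them on the binary endpoints, including both major secondary endpoints analysed in Part 3. The parts of the protocol definition tied to stopping study agent have little scope, because groups 3a and 3b receive none.
- A reader might say that time to loss of disease control has no rule. It has one that can be derived, and the Re-treatment SAP (5.6.1) describes the withdrawal-phase analysis in the same way. The wording is only untidy, since 5.1.8 uses the term observed cases for data that are not set to missing.
- The protocol does not tie treatment failure to time-to-event endpoints, and its own event is PASI >5. A composite event is thus one way to deliver the promised analysis, and belongs beside the main definition.
- The treatment-free endpoint is an addition of the SAP. The two SAPs' stop-date rules differ partly because the phases have different baselines and questions.
- PASI ≤5 at weeks 116, 164 and 220 is planned with both non-responder imputation and observed cases. This gives an indirect view of starters, though imputation also fails other missing subjects.
- With 5 starters the effect is small beside sampling error: the approximate 95% half-width around 46/273 is 1.96 × √(0.168 × 0.832/273) = 4.4 points.
- The Overall safety SAP, dated April 2025, describes the week-220 Part 3 analysis as performed, so a new event definition would now be post hoc.

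None of this supplies the missing analysis, corrects Appendix 2, or gives a date for starters in the treatment-free endpoint.

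**Conclusion.** The concern holds in limited form and should be fixed. A firm protocol commitment was not carried into any supplied SAP and is not listed among the changes. The practical loss is confined to the continuous and time-to-event analyses, and it is clearest for the treatment-free period.

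The only exact figure is 0.37 points per non-re-treated starter on a crude 16.8%. The Kaplan-Meier differences of roughly 0.3 to 2.8 points rest on assumed counts of 5 to 20 and on assumed timing, and are illustrations. If there were no starters, no estimate changes and only the disclosure gap remains. The documents do not support a claim that the Part 3 results are materially biased. Part 3 is exploratory with nominal p-values (Part 3 SAP 5.1), and the week-68 primary result is not affected.

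**What to change.** 1. Keep PASI >5 as the main event. Add the supplementary treatment-failure analysis, including time to loss of disease control with the event defined as the first of PASI >5 or start of a prohibited antipsoriatic therapy. Write the rules in 5.1.6 and 5.1.7, and say how the parts about stopping study agent apply to groups that receive none. Label the analysis post hoc if the week-220 analysis is already done.
2. In any case, list the departure in Appendix 2 or in the study report.
3. In 5.6, state the event status and censoring date for starters in the treatment-free endpoint.
4. In 5.1.8, state whether a PASI >5 seen after the prohibited therapy has stopped counts as an event, or explain why the rule differs from that in the Re-treatment SAP.

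The cost is some wording, one entry in the change list, and one or two extra Kaplan-Meier and Cox tables. The flag for prohibited therapy already exists in the deviations data set. The supplementary estimates will be slightly less favourable if there were any starters.
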